6.12. Health Outcomes/ Quality of Life Analyses

The European Quality of Life - 5 dimension (EQ-5D) questionnaire consists of five items: mobility, self-care, usual activities, pain/discomfort, and anxiety/depression. In addition, a Quality of Life "thermometer" visual analog scale (VAS) is presented that is rated from 0 to 100. For each item patients will choose one of the three options that best described the status. The three options reflecting increasing degrees of difficulty are coded as 1, 2, and 3. Scores from the five items form a five-digit code that describes the respondent's health state. This five-digit code will be then converted to a weighted index (called EQ-5D index) using Japanese population values. The change from baseline to endpoint in the EQ-5D index and VAS score will be analyzed by the ANCOVA model (as described in [Section 6.10](#)). Missing data will be imputed with LOCF method.

6.13. Safety Analyses

Safety will be assessed by summarizing and analyzing extent of exposure, AEs (SAEs, TEAEs, and adverse drug reactions), discontinuations due to AEs, Fall Questionnaire, laboratory measurements, vital signs, weight, and electrocardiogram (ECG) results. In addition, suicide risk and suicide-related events (behavior and/or ideation) as assessed by the C-SSRS.

6.13.1. Extent of Exposure

Treatment exposure is defined as the time from when the patient is randomized at Visit 2 and receives study drug until the last treatment dose date.

Treatment exposure will be listed and further summarized by treatment arm based on the safety analysis set. Duration of exposure will be categorized into the following groups: >0 - 14 days, >14 - 28 days, >28 - 42 days, >42 - 56 days, >56 - 84 days, and >84 days. These categories will be summarized as frequency by treatment group. Summary statistics will include mean per patient exposure in days, SD, median, minimum, and maximum.

In addition, a frequency table of doses at visit 4 and visit 5 will be provided.

6.13.2. Adverse Events

An adverse event is any untoward medical event associated with the use of a drug in humans, whether or not it is considered related to a drug. Adverse events will be classified according to the Medical Dictionary for Regulatory Activities (MedDRA) and summarized by treatment group. TEAEs for treatment period will be defined as events that are newly reported or reported

to worsen in severity after the initiation of study drug through the treatment period. TEAEs for tapering period will be defined as events that are newly reported or reported to worsen in severity during the tapering period. Similarly, TEAEs for follow-up period will be defined as events that are newly reported or reported to worsen in severity during the follow-up period. The incidence of patients with at least one TEAE and the incidence of TEAEs by MedDRA preferred term and system organ class will be presented by treatment group. Fisher's exact test will be used for treatment comparison. These analyses will be summarized by treatment period, tapering period and follow-up period separately, and summarized for combined periods (treatment + tapering + follow-up). All the other analyses below will be summarized for combined periods only.

Treatment-Emergent Adverse Drug Reactions (ADR) will be also by summarized using MedDRA Preferred Term by treatment group. Here, Treatment-Emergent ADR means that TEAEs indicated by the investigator on the Case Report Form (CRF) to be possibly related to the study drug. Similarly, summaries of serious adverse event (SAE), AE leading to discontinuation will be provided separately.

The incidence of patients with TEAEs by maximum severity will be summarized by treatment group using MedDRA Preferred Term nested within System Organ Class.

An overview of AEs will be provided. This summary will include the number and percentage of patients who experienced a TEAE, death, SAE, ADRs, AE leading to discontinuation.

By-patient listings of TEAEs, and SAEs (including death) including the same event on several occasions will be presented. The listings will include both preferred term and the original term used by the investigators.

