#### Safety:

- Spontaneously reported AE (including edema), serious adverse events (SAEs), electrocardiograms (ECGs), vital signs, body weight, and laboratory measurements (clinical chemistry, hematology, urinalysis)
- Columbia Suicide Severity Rating Scale (C-SSRS) and self-harm follow-up form
- Fall Questionnaire

Health Outcomes:

• EuroQol 5 Dimension (EQ-5D)

Other Measures (Baseline Only):

- Patient's Global Impressions of Severity
- Clinical Global Impressions of Severity
- Mini-International Neuropsychiatric Interview (MINI): MDD module only

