#### 10.4.3. Safety Monitoring

The Lilly clinical research physician or clinical research scientist will monitor safety data throughout the course of the study.

Edema and its related events will be monitored carefully, per PMDA, because angiotensin converting enzyme inhibitors and thiazolidines are not prohibited in this study. There are precautions for these drugs in the pregabalin PI; however, there is no obvious evidence for the relationship between these drugs and edema. Moreover, there is no report that these drugs will influence the efficacy evaluation for duloxetine and pregabalin.

Lilly will review SAEs within time frames mandated by company procedures. The Lilly clinical research physician will, as is appropriate, consult with the functionally independent Global Patient Safety therapeutic area physician or clinical scientist and Shionogi.

If a study patient experiences elevated ALT or AST >3X ULN, or elevated total bilirubin >2X ULN, clinical and laboratory monitoring should be initiated by the investigator. Details for hepatic monitoring depend upon the severity and persistence of observed laboratory test abnormalities. To ensure patient safety and comply with regulatory guidance, the investigator is to consult with Lilly regarding collection of specific recommended clinical information and follow-up laboratory tests. See Attachment 3.

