## 12.2. Statistical and Analytical Plans

#### 12.2.1. General Considerations

Statistical analysis of this study will be the responsibility of Eli Lilly.

Efficacy analyses will be conducted on the full analysis set (FAS). The FAS includes all data from all randomized patients receiving at least 1 dose of the study drug according to the treatment the patients were assigned. When mean change from baseline to endpoint is assessed, data will be included in the analysis only if there is a baseline and a corresponding postbaseline measure.

Analyses based on the per-protocol set (PPS) will be performed to examine the robustness of the primary efficacy analysis. The PPS will be defined as a subset of patients in FAS who did not have major protocol deviations.

Safety analyses will be conducted on the safety analysis set. This set includes all randomized patients who received at least 1 dose of study drug. Safety analyses will be based on the treatment the patients actually received.

All tests of hypotheses will be considered statistically significant if the 2-sided p-value is <0.05, unless otherwise stated. No adjustments for multiple comparisons will be made.

Any change to the data analysis methods described in the protocol will require an amendment ONLY if it changes a principal feature of the protocol. Any other change to the data analysis methods described in the protocol, and the justification for making the change, will be described in the clinical study report. Additional exploratory analyses of the data will be conducted as deemed appropriate.

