## 12.2.9. Safety Analyses

Safety will be assessed by summarizing and analyzing AEs (SAEs, TEAEs, adverse drug reactions), discontinuations due to AEs, Fall Questionnaire, laboratory measurements, vital signs, weight, and ECGs. In addition, suicide risk and suicide-related events (behavior and/or ideation) as assessed by the C-SSRS.

For key variables, statistical comparison between treatments will be conducted. For binomial data, such as the proportion of patients with TEAEs, etc, Fisher's exact test will be used. For continuous data, such as change from baseline-to-endpoint (LOCF) in laboratory measurements, etc, ANCOVA, including treatment and baseline value in the model, will be used.

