4.2. Secondary Objectives

[figure not shown]
The secondary objectives of the study are as follows:

- To compare the efficacy of duloxetine (40 to 60 mg/day, orally) versus pregabalin (300 to 600 mg/day, orally) for the treatment of patients with DPNP as measured by:
 - Patient Global Impression of Improvement (PGI-I)
 - Brief Pain Inventory-Severity and Interference rating short form (BPI-SF)
 - Weekly mean of night pain and 24-hour worst daily pain scores measured using an 11-point NRS in the daily patient diary
 - Response to treatment, defined by a 30% and 50% reduction of the weekly mean of the 24-hour average pain score measured using an 11-point NRS in the daily patient diary
 - Neuropathic Pain Symptom Inventory (NPSI)
 - Clinical Global Impressions of Improvement (CGI-I)
 - EuroQol 5 Dimension (EQ-5D)
 - Beck Depression Inventory-II (BDI-II) Total score
- To evaluate the safety and tolerability of duloxetine compared with pregabalin for the treatment of patients with DPNP as measured by frequencies of treatment-emergent adverse events (TEAEs), including edema, the discontinuation rates due to adverse events (AEs), and clinical laboratory tests (including hemoglobin A1c [HbA1c] and glucose).

5. Study Design

Study F1J-JE-HMHA (1413N0841) is a post-marketing, Phase 4, multicenter, randomized, double-blind, parallel-group, flexible-dose, comparative study to assess the noninferiority of duloxetine (40 to 60 mg/day) compared with pregabalin (300 to 600 mg/day) for 12 weeks in approximately 286 adult outpatients with DPNP (143 patients per arm).

Figure HMHA.1 illustrates the study design, which includes a screening period (approximately 1 to 2 weeks), treatment period (12 weeks), tapering period (1 week), and follow-up period (1 week). The study periods are further described below.

Dosage is shown as mg/day. Duloxetine will be administered once daily (QD) and Pregabalin will be administered twice daily (BID).

Figure HMHA.1. Illustration of study design for Clinical Protocol F1J-JE-HMHA (1413N0841).

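### Edema is the only adverse event named in the safety objective, but the SAP plans no count or test of patients with any edema event

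*SAP*

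**What the plan says.** The safety objective in Protocol 6.2, repeated in SAP 4.2, is measured by "frequencies of treatment-emergent adverse events (TEAEs), including edema", by discontinuations due to adverse events and by laboratory tests. No other adverse event is named there. The evaluation criteria in the protocol synopsis list "Spontaneously reported AE (including edema), serious adverse events (SAEs", so edema reaches the database as an ordinary coded adverse event, without an instrument of its own. Protocol 10.4.3 adds: "Edema and its related events will be monitored carefully, per PMDA".

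The analysis text is generic. Protocol 12.2.9 says: "For binomial data, such as the proportion of patients with TEAEs, etc, Fisher's exact test will be used". SAP 6.13.2 plans the incidence of any TEAE, and then "the incidence of TEAEs by MedDRA preferred term and system organ class will be presented by treatment group". On how the arms are compared, the same section states: "Fisher's exact test will be used for treatment comparison". Maximum severity is tabulated "using MedDRA Preferred Term nested within System Organ Class". Adverse drug reactions are summarised by preferred term, serious events and discontinuations have their own summaries, and by-patient listings show preferred and verbatim terms.

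Within the SAP, edema appears only in the objective. Neither document contains an edema term list, a grouped edema variable, or a count or test of patients with any edema event.

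**The concern.** The objective names edema, and the protocol describes it as a group of events, so the natural question is how many patients in each arm had at least one such event. The planned tables give one row per preferred term, which can be too fine, and one row per organ class, which mixes edema with unrelated events. The other items in the same objective do have a matching analysis: discontinuations due to adverse events in SAP 6.13.2, and HbA1c and glucose in 6.13.4. Suicidality and falls have sections of their own (6.13.5 and 6.13.6).

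Two things are at stake. A difference between arms could be spread over sparse rows, none of which looks remarkable. And a reader who wants the edema incidence cannot get it from the tables, because row counts do not add up to patients.

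**Working it through.** **Inputs.** From the documents: 143 patients per arm (SAP section 5); Fisher's exact test (SAP 6.13.2); the significance rule "All tests of hypotheses will be considered statistically significant if the 2-sided p-value is <0.05, unless otherwise stated" (Protocol 12.2.1, repeated in SAP 6.2); no multiplicity adjustment (SAP 6.2). Assumed, because the documents give no figure: the edema rates and the way events divide among preferred terms.

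**The plan's own figure.** The only sample-size calculation is for the primary endpoint. n per arm = 2(1.960 + 0.842)² × 1.82² / (0.51 + 0.1)² = 139.7, so 140 by the normal approximation. With the noncentral t distribution, 140 per arm gives 79.8% power and 141 gives 80.1%, so the stated 141 is reproduced. It says nothing about power for edema.

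**Step 1, grouped test.** Power = Σ Bin(x; 143, p₁) Bin(y; 143, p₂), summed over all tables (x, y) with a two-sided Fisher p below 0.05.

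**Step 2, one term.** If events divide equally over k terms, the same sum with rates p₁/k and p₂/k gives the power q of one term's row.

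**Step 3, any term.** Every row is tested without adjustment, so the like-for-like figure is the chance that at least one edema row is significant. Treating rows as independent, this is 1 − (1 − q)^k. For 12% against 2%: 1 − (1 − 0.531)² = 0.78 and 1 − (1 − 0.287)³ = 0.64. A simulation with one term per patient gives 0.79 and 0.65. The any-term columns below show the formula value, then the simulated value.

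| Assumed rates | Grouped | One of 2 terms | One of 3 terms | Any of 2 terms | Any of 3 terms | Single term with 90% of events |
|---|---|---|---|---|---|---|
| 12% vs 2% | 91% | 53% | 29% | 78%, 79% | 64%, 65% | 87% |
| 10% vs 3% | 60% | 25% | 12% | 44%, 45% | 33%, 33% | 54% |
| 9% vs 2% | 68% | 29% | 13% | 49%, 50% | 33%, 34% | 61% |

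On the simulated values, the loss against the grouped test is about 12 to 18 points with two equal terms and about 26 to 34 points with three. With one term holding 90% of events, unrounded power falls from 90.9% to 86.7%, from 59.8% to 53.5% and from 67.6% to 61.2%, that is, by about 4 to 6 points.

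**Step 4, one data set.** Suppose 3 patients in one arm and 14 in the other have edema. The grouped Fisher p is 0.010. Split over three terms as 1 vs 5, 1 vs 5 and 1 vs 4, the p values are 0.21, 0.21 and 0.37.

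**Step 5, the count.** Rows of 5, 5 and 4 in one arm are compatible with anything from 5 patients (all overlapping) to 14 (no overlap), that is, 5/143 = 3.5% to 14/143 = 9.8%. The preferred-term table cannot distinguish these.

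**The case against.** The objective lists edema within TEAEs, not as a composite endpoint, and SAP 6.13.2 does deliver TEAE frequencies by arm with a test. A reader might infer that the SAP leaves the objective unanswered. That goes too far: it is answered, but in pieces. Nor is the comparison by preferred term and organ class the only adverse-event output. The plan also has drug reactions, severity, serious events, discontinuations and by-patient listings, and from the listings each patient with edema could be counted once.

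The sentence in Protocol 10.4.3 is about monitoring during the trial. A reader might infer that the regulator asked for a pooled edema comparison; the documents show no such request. A display by use of the two drug classes named there might also seem called for. The objective does not ask for it, and the same paragraph says there is no obvious evidence linking those drugs to edema.

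On size, it is tempting to set 91% grouped power against the 53% or 29% of a single row. That overstates the loss, because the SAP tests all the rows. Equal splitting is also unfavourable to the plan, since coding may put nearly all cases under one term.

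These points limit the concern without removing it. The listings and the allowance for exploratory analyses in SAP 6.2 would permit a grouped count, but its term list could then be chosen after unblinding. The any-term chance is lower than the grouped power in every scenario shown, although it draws on several unadjusted tests.

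**Conclusion.** The point holds as a gap between a named objective and its planned analysis. Edema is singled out in the objective and described as a group of events in Protocol 10.4.3, but no prespecified result gives the number of patients per arm with any such event or tests it. This textual finding rests on no assumption about rates.

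The cost in power is conditional. Under the assumed rates it runs from about 4 to 6 points when one term holds 90% of events to about 26 to 34 points when three terms share them equally. The documents do not show where in that range the trial would fall, so they do not support a claim that the comparison is severely weakened. The matter concerns a secondary safety comparison for which the trial was not sized, and it does not bear on the primary non-inferiority conclusion.

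**What to change.** Add to SAP 6.13.2 one grouped variable, edema and related events, with its list of preferred terms fixed at blinded review before database lock. Report the number and percentage of patients per arm with at least one such TEAE, each patient counted once, with Fisher's exact test as for the other TEAEs. Preferably add the risk difference with its 95% confidence interval. Keep the preferred-term and organ-class tables as planned. No display by concomitant drug class is needed.

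The cost is one extra table from data already coded, and agreement on the term list before unblinding.

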#### 10.4.1. Adverse Events

The sponsor has standards for reporting AEs that are to be followed, regardless of applicable regulatory requirements that may be less stringent.

Cases of pregnancy that occur during maternal or paternal exposures to study drug should be reported. Data on fetal outcome and breast-feeding are collected for regulatory reporting and drug safety evaluation.

Study site personnel will record the occurrence and nature of each patient's preexisting conditions, including clinically significant signs and symptoms of the disease under treatment in the study.

After the ICF is signed, site personnel will record any change in the condition(s) and the occurrence and nature of any AEs. All AEs related to protocol procedures are reported to the sponsor via electronic data entry (Inform). In addition, all AEs occurring after the patient receives the first dose of study drug must be reported to the sponsor or its designee via electronic data entry.

Any clinically significant findings from ECGs, labs, vital sign measurements, and other procedures that result in a diagnosis should be reported to sponsor.

Investigators will be instructed to report to the sponsor their assessment of the potential relatedness of each AE to protocol procedure, studied disease state, study drug, via electronic data entry/designated data transmission methods.

The investigator decides whether he or she interprets the observed AEs as either related to disease, to the study medication, study procedure, or other concomitant treatment or pathologies. To assess the relationship of the AE to the study drug, the following terminologies are defined:

- **Related**: a direct cause-and-effect relationship between the study treatment and the AE is likely
- **Possibly related**: a cause-and-effect relationship between the study treatment and the AE has not been demonstrated at this time and is not probable, but is also not impossible
- **Unrelated**: without question, the AE is definitely not associated with the study treatment

As per sponsor's SOPs, all "related" and "possibly related" AEs and SAEs will be defined as related to study drug.

Adverse events that have occurred during the time from Visit 1 to the follow-up visit (Visit 301), are surveyed (Attachment 1).

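### SAP 6.13.2 defines adverse drug reactions by one of the two causality grades that Protocol 10.4.1 counts as drug-related

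*SAP*

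**What the plan says.** Protocol 10.4.1 sets out how investigators judge causality. It introduces the scale with "To assess the relationship of the AE to the study drug, the following terminologies are defined" and gives three grades:

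- **Related** is the upper grade, used where "a direct cause-and-effect relationship between the study treatment and the AE is likely".
- **Possibly related** is the middle grade, used where "a cause-and-effect relationship between the study treatment and the AE has not been demonstrated at this time and is not probable", though not impossible either.
- **Unrelated** is the lowest grade, used where "without question, the AE is definitely not associated with the study treatment".

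It then gives a combining rule: "all 'related' and 'possibly related' AEs and SAEs will be defined as related to study drug".

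SAP 6.13.2 defines the analysis category: "Treatment-Emergent ADR means that TEAEs indicated by the investigator on the Case Report Form (CRF) to be possibly related to the study drug". That category feeds an ADR table by preferred term and treatment group, and one entry of the AE overview: "This summary will include the number and percentage of patients who experienced a TEAE, death, SAE, ADRs, AE leading to discontinuation".

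The protocol synopsis, Protocol 12.2.9 and SAP 6.13 list adverse drug reactions among the things to be summarized but do not define them. The SAP 6.13.2 sentence is the only definition in either document.

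**The concern.** The SAP's phrase is also the name of a protocol grade, and that grade is defined so as to exclude probable causation. Related and Possibly related therefore do not overlap: an event graded Related is not also graded Possibly related. A programmer who selects records by the category of that name would build the ADR table from events whose causal link the investigator thought improbable, and would drop those whose link the investigator thought likely.

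At stake is what the ADR summaries mean. A reader of the study report would take them to show everything investigators attributed to the drug, which is what the protocol's combining rule promises. The by-patient listings in SAP 6.13.2 are described as giving the preferred and original terms. Causality is not mentioned, so the plan does not show that a reader could recover the omitted events from them.

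**Working it through.** No formula applies here. The check is a comparison of the two definitions, followed by a count of the outputs that depend on them.

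**1. The two definitions side by side**

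| Causality grade (Protocol 10.4.1) | Counted as drug-related by the protocol | Named in the SAP 6.13.2 definition |
|---|---|---|
| Related | yes | no |
| Possibly related | yes | yes |
| Unrelated | no | no |

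The protocol has 3 grades and counts 2 as drug-related. The SAP names 1 of those 2, so 2 − 1 = 1 drug-related grade is unnamed, and it is the stronger one.

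**2. Whether another provision closes the gap**

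- The other places that mention adverse drug reactions (protocol synopsis, Protocol 12.2.9, SAP 6.13) only list them.
- SAP 6.13.2 does not refer to Protocol 10.4.1.
- SAP 6.2 says that changes to the protocol's analysis methods will be described and justified in the SAP and the study report. The SAP describes no change to the causality rule. In the SAP revision history, the only entry for 6.13.2 concerns the wording on AEs leading to discontinuation.

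The narrower wording therefore looks like a drafting gap and not a declared decision.

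**3. Outputs that use the definition**

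- ADR table by preferred term: 1 table.
- AE overview: the entries are TEAE, death, SAE, ADRs and AE leading to discontinuation, which makes 5. One of the 5 uses the definition.
- Secondary safety objective (Protocol 6.2): the measures are TEAE frequencies, discontinuation rates due to AEs, and laboratory tests, which makes 3. None of the 3 uses it.

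**4. What each reading would do**

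| Reading of the SAP sentence | Effect on ADR counts |
|---|---|
| The protocol grade of that name only | All TEAEs graded Related are omitted |
| A threshold: at least possibly related | None |
| A single yes/no item on the CRF | None |

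**5. Size of the undercount on the first reading**

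This would need the number of TEAEs, or of patients with TEAEs, in each grade. The documents give neither that split nor the CRF item, so I have computed no figure. The undercount is zero on the other two readings.

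**The case against.** The case for leaving the text alone has four parts.

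**The protocol already settles it.** The combining rule in Protocol 10.4.1 applies to the whole study, and the SAP declares no departure from it. This has weight, but Protocol 10.4.1 never uses the term ADR, and SAP 6.13.2 supplies its own definition in words that differ from the rule. A programmer works from the SAP definition.

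**The harmful reading is the less natural one.** The SAP phrase is in lower case and unquoted. In ordinary English, an event judged likely to be caused by the drug is also at least possibly related. Protocol 10.4.1 itself uses looser language when it asks investigators to "report to the sponsor their assessment of the potential relatedness of each AE". An ADR table that kept improbable links and dropped likely ones would be perverse, and the authors are unlikely to have intended it. I accept all of that as evidence of intent. It does not alter the fact that the phrase is the exact name of a protocol grade, or that the SAP does not say which sense applies.

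**The CRF has not been seen.** The definition rests on what the investigator marks on the CRF. If that is one yes/no box, there is no separate Related category to lose. This stands, and it is why the effect cannot be claimed as certain.

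**The reach is small.** Even on the worst reading, every event graded Related still appears in the TEAE incidence tables, the maximum-severity table and the TEAE listings. This also stands. What would be lost is their identification as drug-related in the ADR outputs.

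Together these arguments limit the weight of the point, but they do not make the two definitions agree.

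**Conclusion.** The point holds as a minor inconsistency. Applied as written on the protocol's own scale, the SAP definition covers one of the two grades that the protocol treats as drug-related and omits the stronger one. The consequence is confined to the ADR table by preferred term and one of five entries in the AE overview. The primary analysis, the TEAE, SAE and discontinuation summaries, and the secondary safety measures are unaffected.

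Any actual undercount depends on two conditions that the documents do not settle: that the CRF records the three protocol grades separately, and that the SAP phrase is programmed as the grade of that name. If either fails, no number changes. Confidence that the texts conflict is high. Confidence that the conflict would reach a table is only moderate. It should still be corrected, because a definition ought not to depend on guessing what its authors meant.

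**What to change.** In SAP 6.13.2, replace the definition with: *Treatment-emergent ADRs are TEAEs that the investigator assessed as related or possibly related to study drug (Protocol 10.4.1).* State that the same definition governs both the ADR table by preferred term and the ADR entry of the AE overview. If the CRF item turns out to be a single yes/no, say so in the same place and define the category by a yes.

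The cost is one sentence in the SAP and a check that the programming specification matches it. It needs no new data and no change to the design or the protocol. If the authors meant the broader sense all along, no result changes.
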